14) The week 48/50 EOS assessments only apply to patients who completed the study per protocol. The assessments are not required for subjects who have undergone ETD assessments and continued in the study without study treatment.

15) ETD: Early treatment discontinuation applies to subjects who discontinue early from study treatment and continue in the study. The assessments should be performed 4 weeks after the last injection of study drug. This can occur at any time point.

16) For patients who continue in the study after ETD and up to Week 48/50 (end of study) while patient is on standard of care. Additional safety assessments and imaging can also be performed if required, as per investigators discretion. In addition, after ETD, subjects are not required to attend the mandatory visits at Week 16 and Week 48/50. The last visit should be at week 48. This can occur at any time point.

Assessments in the fellow eye

The fellow eye will be examined (data collected and analyzed) only at the Screening/Baseline and the Week 48/EOS visits as follows:

- At Screening/Baseline: BCVA, ophthalmic examination, [REDACTED] OCT, [REDACTED].
- At Week 48/EOS: BCVA, ophthalmic examination, [REDACTED] OCT [REDACTED].

Other assessments of the fellow eye may be performed at the Investigator's discretion in accordance with routine practice at other time points; however, these will not be collected or analyzed in this study.

All data obtained from these assessments must be supported in the patient's source documentation.

Concerning Odysight® optimal self-assessment, only best-corrected near visual acuity (BCNVA) for the study eye will be analyzed. It is not requested for the purpose of this study to do any self-assessment measure of the fellow eye.

Unscheduled visits

For patients who return to the study site before the next scheduled study visit, the Investigator will capture the unscheduled visit in the eCRF only in the case of a clinically significant abnormality finding.

If this finding leads to an AE and/or the decision to treat the patient prior to the next scheduled treatment, all the procedures listed for the interim visit need to be conducted and captured in the eCRF.

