The fellow eye will be examined only at Screening/Baseline and Week 48/EOS visits. Only best corrected near visual acuity (BCNVA) for the fellow eye will be analyzed. It is not requested for the purpose of this study to do any self-assessment measure of the fellow eye.

Disease activity criteria: Disease activity criteria will be assessed by the investigator based on whether nAMD is still active or has been re-activated. Guidance for the investigator is as follows (disease is active if at least one of the following criteria is observed by the investigator):

- BCVA decrease \geq 5 letters from the best value since Baseline due to disease activity.
- Any significant increase in CRT (based on investigator assessment).
- Retinal hemorrhage.
- Intraretinal fluid or SRF due to disease activity (degenerative cysts allowed).
- Increase of sub-RPE fluid.

These criteria are for guidance only, the investigator may define disease activity based on his/her own assessment.

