2.15 Interim analysis

An interim analysis was performed when the last patient included completed the Week-16 visit. Patients remained in the study and continued to receive treatment through the maximum planned duration of treatment of 44/46 weeks to allow for further evaluation of efficacy and safety.

3 Sample size calculation

The sample size calculation is based on the hypothesis of 25% to 35% of patients with no disease activity at Week 16. The sample size analyses were performed before the USM were introduced.

Table 3-1 Confidence intervals for proportions (2 sided)

Confidence level	Sample size (N)	Expected proportion	Target distance from proportion to limit
0.950	250	0.25	0.054
0.950	300	0.25	0.049
0.950	325	0.25	0.047
0.950	400	0.25	0.042
0.950	250	0.30	0.057
0.950	300	0.30	0.052
0.950	325	0.30	0.050
0.950	400	0.30	0.045
0.950	250	0.35	0.059
0.950	300	0.35	0.054
0.950	325	0.35	0.052
0.950	400	0.35	0.047

A sample size of 250 to 400 patients produces a 2-sided 95% confidence interval with a distance from the proportion to the limits ranges from 0.042 to 0.059 when the estimated proportion varies from 0.25 to 0.35 (nQuery Advisor version 7.0).

In the HAWK and HARRIER studies, the proportion of naïve nAMD patients treated with brolucizumab who had disease activity at Week 16 was 30% less than for patients treated by aflibercept.

To determine a similar 30% proportion of patients with no disease activity at Week 16 in this pretreated study with a precision of 5% and alpha 5% (2-sided 95% confidence interval of width 11%), a total of 265 patients have to be observed in this study.

Slow recruitment rate was observed in conduct phase of study due to COVID-19, therefore, the sample size was adjusted. The adjusted sample size was significant enough to provide 95% confidence interval.

Considering a dropout rate of 10%, a total of 295 patients will be included.

4 Change to protocol specified analyses

Not applicable

5 Appendix

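### SAP 2.1.1 names the fellow eye for the near-vision (BCNVA) analysis, whereas the protocol names the study eye and neither document requests fellow-eye self-assessment

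*SAP*

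**What the plan says.** The final SAP, section 2.1.1, in the paragraph defining study eye and fellow eye, says: "Only best corrected near visual acuity (BCNVA) for the fellow eye will be analyzed". The next sentence reads: "It is not requested for the purpose of this study to do any self-assessment measure of the fellow eye". The interim SAP, section 2.1.1, has the same two sentences.

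Protocol section 8, under the subheading on assessments in the fellow eye, first covers clinic assessments: "The fellow eye will be examined (data collected and analyzed) only at the Screening/Baseline and the Week 48/EOS visits". The visible items listed there are BCVA, ophthalmic examination and OCT; some items are redacted. It then turns to the Odysight self-assessment and says that "only best-corrected near visual acuity (BCNVA) for the study eye will be analyzed". It closes with the same sentence as the SAP, that fellow-eye self-assessment is not requested. The protocol's printed adjective for the self-assessment is optimal. I read it as optional, since no visible row of Table 8-1 schedules it.

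The SAP section headed "4 Change to protocol specified analyses" is marked as not applicable in both the final and the interim SAP.

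**The concern.** The SAP sentence differs from the protocol sentence in two ways: the eye is reversed, and the opening words that tie the rule to Odysight are gone.

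The reversed eye matters because BCNVA is the only measure that the protocol's Odysight sentence says will be analysed, and it is to be analysed in the eye receiving brolucizumab. A programmer who took SAP 2.1.1 at its word would look for near-vision data in the untreated eye, where the study does not ask for them, and would have no instruction to summarise the treated eye.

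The lost qualifier matters because the sentence can then be read as a general rule that BCNVA is the only fellow-eye variable analysed. That is a different error from the first, and it conflicts with the SAP's own baseline section.

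**Working it through.** No arithmetic applies: no sample size, error rate or effect size enters the point. The check is a comparison of current text with current text.

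**1. Eye named for BCNVA**

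| Source | Eye analysed | Fellow-eye self-assessment |
|---|---|---|
| Protocol section 8 | Study eye | Not requested |
| Final SAP 2.1.1 | Fellow eye | Not requested |
| Interim SAP 2.1.1 | Fellow eye | Not requested |

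The protocol row is coherent: the eye analysed is the eye for which data may exist. Each SAP row is not: the eye analysed is the one for which the following sentence says data are not sought.

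**2. Was the switch declared?** Section 4 of both SAPs records no departure from the protocol's analyses. A deliberate change of eye would belong there.

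**3. What the word only restricts.** The SAP sentence allows two readings.
- It may restrict whose BCNVA is analysed. Study-eye BCNVA is then excluded, against protocol section 8.
- It may restrict which fellow-eye variable is analysed. Study-eye BCNVA is then not barred, but it is not provided for either. This reading also conflicts with SAP 2.4.4, which summarises baseline characteristics, including BCVA and OCT findings, for the study eye and, where applicable, the fellow eye.

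Neither reading agrees with the protocol. Restoring both the qualifier and the eye removes both.

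**4. Likely origin.** The SAP text is almost word for word the protocol's, with one word exchanged. The same SAP paragraph has another departure: it recommends the right eye when both eyes are eligible, whereas protocol section 5 recommends it when both have the same BCVA. A copying slip is the natural explanation, but this is inference.

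**5. What the rule feeds.** BCNVA is absent from the visible objectives and endpoints (protocol Table 2-1 and SAP section 1.2) and from the visible rows of protocol Table 8-1. No visible SAP section specifies a BCNVA table or model. The primary analysis (SAP 2.6.1) and the visible secondary efficacy analyses (SAP 2.7.1) are each expressly limited to the study eye. The self-assessment has still left a trace in the current SAP: deviation OTHER05 in Table 5-1 concerns Odysight use without consent.

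**The case against.** The best answer is that this is a one-word slip in a definitions paragraph, that the protocol makes the intended eye plain, and that no visible analysis depends on it. A block after SAP 2.11 is redacted and may contain a BCNVA section naming the study eye. The SAP's change history records that correlation and Bland-Altman code was dropped. If that concerned BCNVA, which cannot be seen, the near-vision analysis may have been cut back. All of this limits the impact, and I accept it. It does not rescue the sentence: if a BCNVA section exists, 2.1.1 would contradict it, and if the analysis was dropped, the sentence should have been deleted.

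A reader might infer more than the documents support.

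- **That fellow-eye BCVA and OCT are dropped.** SAP 2.4.4 keeps the baseline fellow-eye summaries. Sections 2.4.5, 2.5.2, 2.5.3 and 2.9.1 report fellow-eye medical history, ocular medications, procedures and ocular adverse events. In practice the SAP does not confine fellow-eye reporting to BCNVA.
- **That up to 295 patients are affected at two visits.** This fails at baseline for the reason just given. At Week 48 the planned total is no guide, because patients who stop treatment early need not attend (protocol 9.1.1).
- **That the SAP must add a Week 48 fellow-eye summary.** Protocol section 8 does say, in a parenthesis, that fellow-eye data are analysed, but protocol 12.5 restricts eye-level secondary efficacy analyses to the study eye. That tension lies within the protocol, and a new summary would go beyond repairing this sentence.
- **That a fellow-eye BCNVA table would be empty, or that all study-eye BCNVA would be lost.** Data that are not requested may still be entered, and the operative BCNVA text, if any, cannot be seen.

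**Conclusion.** The point holds as an inconsistency between the SAP and the protocol, and between two adjacent SAP sentences. As written, the SAP assigns the near-vision analysis to the eye for which no self-assessment is requested, omits the treated eye, and declares no change.

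The size is small. Only the optional near-vision analysis is affected. Uptake of the self-assessment is not stated, so no patient count can be given. The primary endpoint, the visible secondary endpoints, the safety analyses and the sample size do not depend on it. The interim SAP repeats the error with little consequence: its efficacy data stop at Week 16, its visible endpoints do not include BCNVA, and final SAP 2.15 reports the interim analysis as already done.

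The conclusion assumes that the protocol wording is the intended one, which the undeclared switch and the sentence on fellow-eye self-assessment both support, and that no redacted text in the SAP overrides section 2.1.1.

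**What to change.** In final SAP 2.1.1, replace the BCNVA sentence with the protocol's rule, keeping its opening reference to the Odysight self-assessment and naming the study eye: "only best-corrected near visual acuity (BCNVA) for the study eye will be analyzed". The sentence that follows, on fellow-eye self-assessment, can stay. Restoring the qualifier also removes the conflict with SAP 2.4.4.

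If the sponsor did intend to analyse the fellow eye, the change should instead be declared and justified in SAP section 4, and the sentence saying that fellow-eye self-assessment is not requested reconciled with it. If the near-vision analysis was dropped, delete the BCNVA sentence and record that in section 4.

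For the interim SAP, a note for the record is enough. The cost is one sentence and a check that any BCNVA section or table shell names the same eye; no new data are needed.

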2.2 Visit windows for data analysis

Visit windows will be used for the data analysis, as per the planned visits in the protocol. During the q4w/q8w/q12w phase, i.e., from Week 16 to Week 44, the treatment visit intervals will be determined by the investigator, based on the patient's disease activity.

Table 2-1 Assessment windows for scheduled visits

Analysis Visit	Week	Scheduled Day	Visit Window
Screening/Baseline	BL	1	-14 days to Day 1*
Week 4	4	28	Day 22 – 34
Week 8	8	56	Day 50 – 62
Week 12	12	84	Day 78 – 90
Week 14	14	98	Day 92 – 104
Week 16	16	112	Day 106 – 118
Week 18	18	126	Day 120 – 132
Week 20	20	140	Day 134 – 146
Week 22	22	154	Day 148 – 160
Week 24	24	168	Day 162 – 174
Week 26	26	182	Day 176 – 188
Week 28	28	196	Day 190 – 202
Week 30	30	210	Day 204 – 216
Week 32	32	224	Day 218 – 230
Week 34	34	238	Day 232 – 244
Week 36	36	252	Day 246 – 258
Week 38	38	266	Day 260 – 272
Week 40	40	280	Day 274 – 286
Week 42	42	294	Day 288 – 300
Week 44	44	308	Day 302 – 314
Week 46	46	322	Day 316 – 328
Week 48	48	336	Day 330 – 342
Week 50	50	350	Day 344 – 356

* Baseline measurement before the first treatment administration.

The number of weeks between visits will vary depending on the disease activity and length of intervals between injections as determined by disease activity assessment. Study treatment at the optional inspection visits (6 weeks after the last injection when the interval is extended from 4 weeks to 8 weeks, 10 weeks after the last injection when the interval is extended from 8 weeks

to 12 weeks, and 14 weeks from the last injection when the interval is extended from 12 weeks to 16 weeks) is at the discretion of the Investigator based.

According to the patient treatment schedule, the last treatment can be at Week 44 or to Week 46. If the last treatment visit is Week 46, the end of study visit will be at Week 50 (at least 4 weeks after the last injection) instead of Week 48.

If study visit assessments and the corresponding treatment occur on separate days, a repeat safety check-up should be performed prior to treatment of the eye and results documented in the source documents. If any safety concern arises related to the study eye that, in the opinion of the investigator, may be further impacted by the study treatment or injection procedure, treatment needs to be cancelled. Injections are contraindicated in patients with active intraocular or periocular infections and in patients with active intraocular inflammation (IOI); therefore, the investigators must verify that these conditions are not present in the study eye prior to every injection. Any AEs must be recorded in the eCRF.

The injection procedure for brolucizumab will be performed according to local clinical practice. Injections will be administered by the investigator.

Data collected at unscheduled visits will not be used in ‘by-visit’ tabulations or graphs and will be presented in listings.

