A planned study visit schedule will be established at Screening/Baseline/Day 1 for all patients. All post-Screening/Baseline and/or subsequent scheduled visits will be calculated based on the Day 1 visit date. During the Treat-to-Control Phase, from Week 8 to Week 44/46, the treatment visit intervals will be determined by the Investigator, based on the patient's disease activity (see [Section 6.7.2](#)). All efforts should be made to adhere to all scheduled visits and assessments as outlined in the assessment schedule ([Table 8-1](#)).

A \pm 7-day visit window will be allowed should the patient be unable to return per the scheduled visit. All efforts should be made to revert back to the planned visit schedule taking into consideration the restrictions on the minimum treatment interval for the study medication (brolucizumab).

Assessments can be performed on 2 consecutive days in which both days must occur within the visit window.

Treatment is intended to be administered on the day of the study visit, or if this is not possible, within 3 days after the study visit at which the per-protocol assessments took place. If study visit assessments and the corresponding treatment occur on separate days, a repeat safety check-up should be performed prior to treatment of the eye and results documented in the source documents. For all visits, efficacy assessments ([Section 8.3](#)) and safety assessments ([Section 8.4](#)) should be performed prior to any administration of study treatment.

Missed or rescheduled visits should not lead to automatic discontinuation.

If the COVID-19 pandemic limits or prevents on-site study visits, study treatment could not be administered and other study assessments may not be performed. Alternative methods of safety monitoring may be implemented. Depending on local regulations, site capabilities and patient's visit status in the study, phone calls or virtual contacts (e.g. teleconsult) can be performed for safety follow-up for the duration of the pandemic, until it is safe for the participant to visit the site again.

Patients who prematurely discontinue study treatment for any reason should return for the EOS visit assessments as scheduled in [Table 8-1](#), except for patients who withdraw their consent from the study and do not wish to do so (refer to [Section 9.1.2](#)).

Table 8-1 Assessment schedule for the study eye

Period	Treatment Period					Follow-up	
	Initiation Phase			Treat-to-Control Phase			

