2.1.1 General definitions

[figure not shown]
Study treatment: This is a single-arm study and all patients will be treated with brolucizumab 6 mg. Three loading injections (at Screening/Baseline/Day 1, Week 4 and Week 8), followed by a Treat-to-Control (TtC) regimen phase based on disease activity from Week 8 up to Week 44/46 (according to the treatment regimen). The investigator can individualize treatment intervals depending on disease activity, to adjust patient's injection regimen.

Study treatment start and end date: Study treatment start date is defined as the first date study treatment is administered and recorded on the Treatment Administration Record (DAR) Electronic Case Report Form (eCRF) page. Similarly, study treatment end date is defined as the last date of study treatment is administered and recorded on the Study Treatment Completion eCRF page.

Generally, study Day 1 is considered as the day of inclusion of the patient. However in this study, treatment is intended to be administered on the same day or if this is not possible, within 3 days after the day of inclusion of the patient.

Study day will be calculated as ((event date – study treatment start date) + 1 day) for events that occurred on or after study treatment start date (e.g. visit, AEs). For events prior to study treatment start date (e.g. time since diagnosis), study day will be negative and calculated as (event date – study treatment start date).

Baseline and post-baseline: Baseline value refers to the value of the last non-missing measurement collected prior to administration of the first dose of study treatment (Screening or Baseline visit).

A “post-baseline” value refers to a measurement taken after the first dose of study treatment. When assessments and treatments take place on the same day, treatment must occur after completion of the efficacy assessments and pre-injection safety measures (tonometry, slit lamp

[REDACTED]). If study visit assessments and the corresponding treatment occur on separate days, a repeat safety check-up will be performed prior to treatment of the eye and results documented in the source documents. More post-baseline safety measurements will be recorded in source document; visit window will be applied to OCT and IVT visits.

Change from Baseline: The difference of measure between post-baseline and Baseline is called change from Baseline.

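### SAP visit windows are ±6 days around Day 7w, not the protocol's ±7 days from Day 1, so if applied by date they drop or relabel some on-time Week 16 visits; the SAP does not say whether they select the primary record

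*SAP*

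**What the plan says.** **Protocol Section 8.** The schedule is anchored on the first visit: "All post-Screening/Baseline and/or subsequent scheduled visits will be calculated based on the Day 1 visit date". A ± "7-day visit window will be allowed should the patient be unable to return per the scheduled visit".

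**SAP 2.2.** "Visit windows will be used for the data analysis, as per the planned visits in the protocol". Table 2-1 gives Week 16 as scheduled Day 112, window Day 106 to 118. The interim SAP prints the same table. The only assignment rule shown beside it concerns unscheduled visits: "Data collected at unscheduled visits will not be used in" the by-visit tables and graphs.

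**SAP 2.1.1.** "Study day will be calculated as ((event date – study treatment start date) + 1 day", and visits are named among the events covered. The first injection is meant for the inclusion day or, "if this is not possible, within 3 days after the day of inclusion of the patient". On scope, the same section says that the "visit window will be applied to OCT and IVT visits".

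**Primary endpoint.** SAP 2.6.1 (2.7.1 in the interim SAP) takes patients without disease activity at Week 16 over the whole FAS, and also reports the number of evaluable patients. The underlying record is the investigator's: "Disease activity criteria will be assessed by the investigator based on whether nAMD is still active or has been re-activated". Neither section refers to Table 2-1 or to the nominal visit.

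**Related rules.** Protocol 6.7.2.2 uses the Week 8 or Week 14 value when Week 16 is missed. Deviation OTHER14 in SAP Table 5-1 flags only visits more than 7 days off and keeps those patients in every analysis set.

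**The concern.** The table is said to follow the protocol, but neither its width nor its apparent day origin matches. A patient seen on a day the protocol permits, with no deviation recorded, can therefore have no Week 16 record under the table, or have it filed under a neighbouring week.

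The only primary endpoint is status at Week 16. If date windows select the disease-activity record, the text leaves open three treatments of an on-time record that falls outside the row:

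- counted as not controlled, because the denominator is the full FAS;
- dropped as not evaluable;
- replaced by the Week 8 or Week 14 value, if treated as a missed visit under Protocol 6.7.2.2.

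If the windows govern OCT records, the by-visit summaries of CSFT, fluid and dry retina lose the same days. Two programmers working from this text could build different Week 16 datasets.

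**Working it through.** **1. Reproducing the table.** For week w, four constructions were tried on the 22 post-baseline rows (the baseline row has a different form). Week 16 results:

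| Construction | Week 16 window | Rows matched |
|---|---|---|
| 7w ± 7 | 105–119 | none |
| (7w + 1) ± 7, same-day injection | 106–120 | none |
| (7w + 1 − k) ± 7, injection delay k = 1, 2, 3 days | 105–119, 104–118, 103–117 | none |
| 7w ± 6 | 106–118 | 22 of 22 |

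Only ±6 reproduces the printed rows. No section states that half-width.

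**2. On-time days lost at Week 16.** Take the SAP study-day formula (first injection = Day 1) and a first injection k days after the Day 1 visit. A Week 16 visit at offset d (−7 to +7) then falls on study day 112 + d − k + 1. Against Day 106–118:

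| k | Permitted days | Days not labelled Week 16 | Lost |
|---|---|---|---|
| 0 | 106–120 | 119 (no window), 120 (Week 18) | 2 of 15 |
| 1 | 105–119 | 105, 119 (no window) | 2 of 15 |
| 2 | 104–118 | 104 (Week 14), 105 (no window) | 2 of 15 |
| 3 | 103–117 | 103, 104 (Week 14), 105 (no window) | 3 of 15 |

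If Day 112 is instead read as exactly 16 weeks, the permitted days are 105–119 and Days 105 and 119 are lost. The same calculation for Weeks 4, 8 and 48 also loses 2 or 3 of 15 days.

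**3. Gaps.** From Week 14 to Week 50 the uncovered days are 105, 119, …, 343, which is (343 − 105)/14 + 1 = 18 single days.

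**4. Possible size for the primary endpoint.** The documents give no distribution of visit timing. Assumption: whole-day offsets d from −7 to +7, with weights proportional to exp(−d²/(2·SD²)); a true proportion of 30%; same-day injection, so offsets +6 and +7 are lost.

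| SD (days) | Weight at +6 and +7 / total | Share lost | × 265 patients |
|---|---|---|---|
| 2 | 0.0133 / 5.01 | 0.27% | 0.7 |
| 3 | 0.2011 / 7.43 | 2.71% | 7.2 |
| 4 | 0.5409 / 9.42 | 5.74% | 15.2 |

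*Counted as failures, all 265 attending:* shift = 30 × share = 0.08, 0.81 and 1.72 points, giving 29.9%, 29.2% and 28.3%.

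*Counted as failures, FAS of 295 with 265 attending:* the shift due to the windows alone is multiplied by 265/295 = 0.898, giving 0.07, 0.73 and 1.55 points.

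*Dropped, unrelated to outcome:* no shift. The half-width 1.96 × √(0.21/N) goes from 5.52 points at N = 265 to 5.53, 5.59 and 5.68 at N = 264, 258 and 250.

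*One-day delay for everyone, counted as failures over 265:* shares 0.09%, 1.77% and 4.59%; shifts 0.03, 0.53 and 1.38 points. *Three-day delay for everyone (extreme):* shares 1.1%, 6.1% and 10.6%; shifts 0.3, 1.8 and 3.2 points.

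*Replaced by the Week 8 or Week 14 value:* cannot be sized, because the documents do not say how often those assessments agree with Week 16.

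*Nominal visit used:* zero.

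**The case against.** The best defence is that an analysis window need not copy the conduct allowance. SAP 2.2 ties the windows to the planned visits, not expressly to ±7 days. With rows 14 days apart, ±7 windows share a boundary day: a Week 14 visit at +7 and a Week 16 visit at −7 both fall on Day 106. A half-width of 6 removes that overlap and may have been chosen for this reason. That is plausible, but it trades a tie, which a one-line rule resolves, for days that belong to no visit.

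The day origin is also less firm than step 2 implies. Table 2-1 names none. SAP 2.1.1 calls inclusion the usual Day 1 before giving the formula based on first injection, and the protocol also times some later visits from the preceding injection. The results for k = 1 to 3 hold only if visits stay tied to the Day 1 visit. Same-day injection and the exact-16-weeks reading do not need a delay, and both still lose two days.

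The scope wording can be read either way, since Week 16 is itself an OCT and injection visit. The SAPs leave programming specifications to a separate document that is not visible here and may contain the missing rule. OTHER14, which keeps late visits in all analysis sets, sits badly with any intention to discard on-time ones.

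A reader might infer that on-time Week 16 outcomes are certain to be lost, or that 2 of 15 days means about 13% of patients. The documents support neither. The first depends on date windows governing the disease-activity record, which is not stated. The second would need visits spread evenly over the permitted days.

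**Conclusion.** The table is wrong as written. It does not reproduce the protocol's window on any day origin tried and, where applied, leaves 2 or 3 of 15 permitted Week 16 days unassigned or assigned to another week. Whether this reaches the primary endpoint is open, because SAP 2.6.1 names no selection rule.

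If it does, and lost records count as failures, the downward shift is about 0.1 to 1.7 points with all 265 attending, or 0.07 to 1.55 points with a FAS of 295. Both ranges rest on an assumed timing SD of 2 to 4 days, same-day injection and a true 30%. They compare with a planned half-width of 5.5 points (Protocol 12.8). The number of patients affected cannot be known from the documents.

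Nothing in the documents shows that the interim Week 16 result is wrong; it needs a check, not a presumption of error. The point should be corrected because it concerns the sole primary endpoint and is cheap to settle, not because the likely effect is large.

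**What to change.** 1. **Primary record.** State in SAP 2.2 and 2.6.1 that the nominal eCRF Week 16 visit supplies the disease-activity record, and apply the same rule to the other mandatory visits (Weeks 4, 8 and 48/50). Visits more than 7 days off stay flagged under OTHER14. Set an outer limit in advance, or add a sensitivity analysis for them, so that a very late visit does not pass as Week 16 unnoticed.
2. **Scope.** Say whether date windows cover disease activity and BCVA, or only OCT and injection records.
3. **Table 2-1.** Where date windows are kept, count from the Day 1 visit, centre on Day 7w + 1 and make the rows contiguous. Give a tie-break for shared boundary days (for example Days 106 and 120) in favour of the mandatory visit, and a rule for two records in one window.
4. **Interim result.** SAP 2.15 reports that the interim analysis has been performed. Check whether its Week 16 derivation used the date windows. If so, re-derive it and disclose the change as made after the interim analysis.

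The cost is a few sentences and one corrected table in each SAP, plus the derivation check. No new data are needed.
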